4.11 Chart/Record Review Selection

N/A

4.12 Secondary Specimen Collection

N/A

5.0 Special Considerations

5.1 Health Insurance Portability and Accountability Act (HIPAA)

We will be obtaining individually identifiable health information associated with a HIPAA-covered component or entity in the course of the research.

5.2 Family Educational Rights and Privacy Act (FERPA)

N/A

5.3 NJ Access to Medical Research Act

N/A

5.4 Code of Federal Regulations Title 45 Part 46 (Vulnerable Populations)

A. "Special" Classes Of Subjects

- (1) *Pregnant Women: see guidance (HRP-412)*
- (2) *Neonates: see guidance (HRP-413)*
- (3) *Neonates of Uncertain Viability: see guidance (HRP-414)*
- (4) *Prisoners: see guidance (HRP-415)*
- (5) *Children: see guidance (HRP-416)*
- (6) *Cognitively Impaired Adults: see guidance (HRP-417)*

N/A

6.0 Research Data Protection and Reporting

6.1 Data Management and Confidentiality

A. *Describe the data analysis plan, including any statistical procedures.*

Although this pilot study will not be powered to detect significant differences between the intervention and control group, we will conduct descriptive analyses (means, medians, and percentages) and examine group differences (e.g., chi-square, ANOVA, t-tests) to explore possible effects. Additionally, we will track and compare number of sessions completed and dropout using chi-square, Poisson regression, and t-tests.

B. *Provide a power analysis. (As applicable, e.g. quantitative research)*

Since this is a pilot study to determine feasibility and preliminary effect size, the study is not powered to detect significance, but to inform a larger study. A sample size of 31 is adequate for a pilot study.

C. Describe the steps that will be taken to secure the data (e.g., training, authorization of access, password protection, encryption, physical controls, certificates of confidentiality, and separation of identifiers and data) during storage, use, and transmission.

All investigators and research staff will have undergone mandatory education in human research participant protection. To assure confidentiality, data will be secured in a database management system, password protected files, and in secure file cabinets. Data collection forms, databases, and recordings will not include identifiers other than a study ID code. The key to the code will be kept separately in a locked and/or password protected file for no longer than six years. Informed consent forms will be kept separately in a locked file in the same office. Three levels of security are provided to prevent unauthorized persons from accessing the data: password protection, computer or file cabinet locks, and a locked office. In addition we have a Certificate of Confidentiality from the National Institutes of Health that protects study data from subpoena. Access to data will be limited to study investigators and staff. Research data will be kept no longer than 10 years.

D. Describe any procedures that will be used for quality control of collected data.

As we have done in prior studies, a manual of procedures will be developed during the initial start-up period that explicitly describes the specific procedures related to data collection, entry, storage, and quality assurance for both study conditions. Data will be collected by research staff in strict accordance with the study's protocols. All data collection forms will be independently reviewed for quality and consistency by a member of the research team who was not responsible for collecting the source data. The research staff will be trained to avoid omissions in data collection and data entry. Computer entry protocols will be programmed to avoid accidental skipping of question items. We will apply conditional formatting to datasheets to remove the possibility of out of range data. All data on written forms will be entered twice by two separate data entry personnel and compared via a macro we have experience using within Microsoft Excel datasheets other data will be entered directly into a secure Qualtrics databases. Once all data on paper forms is entered, paper forms will be housed at a facility that specializes in the storage of medical/research information. The destruction date of these files will be within 10 years from the termination of the study and will be authorized by the Principal Investigator. Under supervision from [name], the Research Assistant will conduct monthly descriptive summaries on all data to ensure their accuracy. This will not involve completing any statistical comparisons. If problems are noted in data entry (e.g., out of range values, missing values), the Research Assistant and [name] will investigate the root cause, and solutions to rectify the problem will be generated and implemented.

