This is a pilot study designed to determine study feasibility and evaluate the impact of a novel intervention, MORE, on opioid use and chronic pain among individuals receiving methadone maintenance treatment. We will evaluate progression to a larger study based on the success of three key milestones. For the pilot study, we plan to evaluate our ability to recruit participants into the study, defining successful recruitment as 75% or more of our planned sample size by month 7. Retention will be considered successful if 50% of participants attend at least 4 MORE sessions, and will be assessed at month 9. We will evaluate our ability to collect 8-week and 16-week follow up data, defining success as a follow-up rate of 65% of participants at 8-weeks and 50% of participants at 16-weeks assessed at month 11. In addition to evaluating study feasibility through obtaining these milestones, we will obtain information about the efficacy of MORE on opioid use and chronic pain among MMT patients. It is hypothesized that: 1) Participants in MORE will have a longer duration of time to first opioid lapse than TAU participants; 2) Participants in MORE will have a longer duration of time to MMT dropout than TAU

participants; 3) At 8 and 16 –weeks post-enrollment, the MORE group will have fewer days of opioid use and fewer days of any drug use; 4) At 8 and 16 –weeks post-enrollment, the MORE group will have more days of methadone treatment than the TAU group; and 5) At 8 and 16 –weeks post-enrollment, the MORE group will have greater decreases in pain severity and pain interference than the TAU group.

1.2 Research Significance (*Briefly describe the following in 500 words or less*):

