MORE sessions. We will consider our ability to follow participants successful if we obtain 8-week assessments from at least 65% of participants and 16-week assessments from at least 50%. Although we are targeting a follow-up rate in both groups of at least 80% and 75% at 8 and 16 weeks, respectively, we set the benchmarks at 65% and 50% because, again, if necessary, we can adapt follow-up strategies for the next study, based on lessons learned in this study.

Preliminary outcome measures to be assessed during this pilot study will be time until opioid lapse and MMT dropout. Preliminary secondary outcomes will be: days of methadone medication use, days of opioid and other drug use, and changes in pain severity and intensity. Additional measures are described below.

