8	Discussion of how to maintain mindfulness practice; finding a sense of meaning and purpose of life; development of mindful recovery plan; imaginal rehearsal of skill learning; mindful breathing

Treatment as Usual (TAU). In the MMT programs, clients typically come to the clinic regularly (usually 6 days per week at the beginning of treatment) to get their methadone dose; as clients progress through the program and remain abstinent from drugs, they earn "take home doses" that they can take on days that they are not required to come to the clinic. Timing of the initiation of take-home doses and the scheduling of clinic days varies across clinics. Clients see their clinic substance abuse counselor for individual counseling, usually weekly at the beginning of treatment, with decreasing frequency if they remain abstinent and progress through treatment. Depending on clients' stage of MMT and success with remaining abstinent from drugs, they may be required to attend clinic treatment groups. Also, some clients may choose to go to voluntary counseling, educational, or support groups (none of these groups involve coping with pain oriented or are mindfulness-based). All individual treatment characteristics, including methadone dosage, take-home dosing, clinic attendance and attendance at clinic counseling sessions and groups, will be documented for all study participants and entered as covariates in the analyses.

B. Dependent Variables or Outcome Measures

The main objective of this pilot study is to establish study feasibility in recruiting, retaining, and following up with MMT patients in the MORE and TAU interventions. The primary feasibility outcome measures are:

- The number of individuals who express interest in the study and the number who refuse (and reasons for refusal).
- The number of individuals who contact the staff with interest in the study.
- The number of individuals screened and eligible/ineligible.
- The number of individuals consented.
- The number of individuals who refuse participation after/during consent process.
- The number of sessions completed by study participants.
- The number of participants who drop out and reasons for drop out.
- Reasons for missed sessions.
- The number of completed/missed assessments including questionnaire data, drug screens, cognitive tasks, and EMA assessments.

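### Section 6.1 A states no censoring-aware analysis for time to first opioid lapse or time to MMT dropout, and their event rules are incomplete: minor, and cheap to fix

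*Combined protocol and SAP*

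**What the plan says.** Section 1.3 puts two times to event ahead of the preliminary secondary outcomes: "Preliminary outcome measures to be assessed during this pilot study will be time until opioid lapse and MMT dropout". Section 1.1 B states the first hypothesis as "Participants in MORE will have a longer duration of time to first opioid lapse than TAU participants", and the second makes the same claim for MMT dropout.

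For analysis, section 6.1 A plans means, medians and percentages and will "examine group differences (e.g., chi-square, ANOVA, t-tests) to explore possible effects". It adds that "we will track and compare number of sessions completed and dropout using chi-square, Poisson regression, and t-tests", without saying whether this is dropout from MMT or from the study. Section 1.9 B adds linear mixed models for the EMA data. No section mentions censoring or a time-to-event method.

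On event definitions, section 1.9 B gives the data sources for lapse (EMA and timeline follow-back) and counts dropout time from enrollment to the last methadone dose. It codes a positive screen with denied use as use.

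Section 1.6 A says that individual treatment characteristics "will be documented for all study participants and entered as covariates in the analyses". Section 6.1 B gives the purpose: "Since this is a pilot study to determine feasibility and preliminary effect size". Section 1.1 B says of the next stage: "We will evaluate progression to a larger study based on the success of three key milestones".

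**The concern.** Most participants would probably reach week 16 without either event, and some will be lost earlier. Their event times are then known only to exceed the last observation. A t-test on observed days treats those censored times as event times, so any difference between arms in length of follow-up enters the comparison. A chi-square on the proportion with an event also ignores how long each person was observed.

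The definitions are a separate gap. Without a rule for when dropout has occurred, or for dating a lapse seen only on a screen, two analysts could derive different datasets from the same records. The pilot is meant to supply a preliminary effect size for a larger trial (N=150 in section 1.3), and that figure cannot be interpreted or reproduced without these rules.

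**Working it through.** **The plan's own figure.** N=31 comes with no formula, alpha, power or effect size, so only the arm sum can be checked: 15 + 16 = 31. Nothing below changes N.

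**Inputs.** From section 1.2: 50% of those retained in MMT relapse within six months, and about 50% of those starting MMT stop within twelve months. From section 1.3: 16 weeks (112 days) of participation. Assumed here: constant hazards, loss independent of lapse, no drug-use data after loss, and the follow-up rates shown. The section 1.2 rates may not fit this sample, which has at least 3 months in MMT and no abstinence requirement at entry.

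**Event-free at week 16, full follow-up, no effect.**
- Lapse: 0.5^(16/26) = 0.653, so about 31 × 0.347 = 10.8 lapses.
- MMT dropout: 0.5^(16/52) = 0.808, so about 25 of 31 still in treatment and 6.0 dropouts.

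Neither median would be reached.

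**Mean observed lapse days.** Per arm the mean is (1 − exp(−112r))/r, where r = lapse hazard + loss hazard. The TAU lapse hazard is ln 2/182.5 per day. The loss hazard is −ln(follow-up)/112.

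| Follow-up MORE/TAU | No effect: MORE − TAU | HR 0.5: MORE − TAU |
|---|---|---|
| 100%/100% | 0 | 100.9 − 91.2 = 9.7 (true) |
| 75%/75% | 0 | 88.1 − 80.1 = 8.0 |
| 80%/65% | 82.4 − 75.2 = 7.2 | 90.8 − 75.2 = 15.5 |
| 65%/80% | −7.2 | 82.6 − 82.4 = 0.2 |

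(Differences are taken before rounding.) With faster lapse the 7.2 days shrinks to 4.3 (60-day median) or 2.2 (30-day median).

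**Simulation, 6,000 trials of 15 v 16, six-month median.** With no effect and 80%/65% follow-up, the t-test rejects 7.7% and log-rank 4.6%, and the Kaplan-Meier difference is −0.1 days. At HR 0.5, Kaplan-Meier gives 9.5 to 9.7 days across the follow-up patterns. Poisson regression with a log person-time offset also copes under 80%/65%: the median rate ratio is about 1.0 under no effect and about 0.5 at HR 0.5.

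**If loss depends on lapse.** Suppose there is no effect, half of TAU lapsers go silent at lapse and no MORE lapsers do. Kaplan-Meier then shows −9.8 days and log-rank rejects 15.1%. Counting loss as lapse gives −0.1 days and 5.0%. Under independent 80%/65% loss the loss-as-lapse analysis itself shows 7.0 days, so it is a bound and not a correction.

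**Event rules, set side by side.**
- Dropout time ends at the last dose (1.9 B), with no criterion for when dropout has occurred and nothing for someone still dosing at week 16.
- Time is counted from enrollment (1.9 B), but randomization waits until at least 10 are recruited at a clinic (4.3). Events before randomization could therefore be counted.
- Screen-positive use is coded as use (1.9 B) but given no date. The panel detects morphine and oxycodone (1.8 A) and pain medication is recorded (1.9 B), yet no rule covers prescribed opioids.
- Entry does not require abstinence (4.2 D), and nothing says how lapse is handled for someone using opioids at baseline.

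**Precision and covariates.** Expected lapses run from 10.7 (no effect, full follow-up) to 7.4 (HR 0.5, 75% followed). With SE(log HR) ≈ 2/√events and 8.4 lapses (HR 0.5, full follow-up), the SE is 0.69 and the 95% interval is 0.5 × exp(±1.96 × 0.69) = 0.13 to 1.93. Section 1.6 A lists five characteristics (dose, take-home dosing, clinic attendance, counseling sessions, groups). At 7 to 11 lapses that is 1.4 to 2.2 events per covariate.

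**The case against.** The strongest reply is that nothing in the plan is wrong. The list in section 6.1 A is illustrative, so survival methods are not excluded. Poisson regression is named for dropout and, with an offset, is a constant-hazard survival model. A reader might infer that the planned methods cannot handle censoring; the text does not support that. What stands is that the offset and the censoring rule are unstated.

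A reader might also infer that the comparison will be biased. The documents do not predict this. Section 1.3 says "we are targeting a follow-up rate in both groups of at least 80% and 75% at 8 and 16 weeks", and assessment payments and the phone fallback are the same in both arms. Only MORE has weekly sessions with session payments. The 80%/65% contrast is an assumption: in section 1.3 those figures are the 8-week target and benchmark. With equal follow-up, bias under no effect is zero and chi-square performs about as well as log-rank.

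Nor is Kaplan-Meier safe if loss depends on lapse; in that scenario the t-test held 4.6%. The proposed sensitivity analysis amounts to the comparison of mean observed days. That is a reason to report both, not to leave the choice open.

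Two further readings go too far. One is that section 1.9 B deliberately gives retained participants a dropout time; it more naturally describes those who leave, but the rule for the rest is missing. The other is that adjusting for take-home dosing always conditions on the outcome. That holds only for values measured after randomization, and section 1.6 A does not say when they are measured.

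**Conclusion.** The concern holds as a minor improvement to an exploratory analysis. Two outcomes that the plan places first among its clinical measures have no stated censoring-aware analysis, no censoring dates and incomplete event rules.

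The size is conditional. It is zero under no effect with equal follow-up, about 7 days of spurious difference at an assumed 80%/65%, and at HR 0.5 an estimate anywhere from 0.2 to 15.5 days against a true 9.7. These figures rest on the section 1.2 relapse rate as a constant hazard and on loss independent of lapse; continued EMA reporting or faster lapse would reduce them. For MMT dropout no differential bias has been shown; the gap there is the event rule.

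A reader might take this as a threat to the decision on the larger trial. It is not: progression rests on feasibility milestones and the study is expressly unpowered. What is affected is the preliminary effect size.

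**What to change.** Add to section 6.1 A, labelled exploratory:

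- Time to first opioid lapse and time to MMT dropout are summarised by Kaplan-Meier curves, a log-rank test and an unadjusted Cox hazard ratio with 95% CI (or Poisson regression with a log person-time offset).
- Time runs from randomization, or the plan states how events between enrollment and randomization are handled. Since assessments are scheduled from baseline, say which date week 16 refers to.
- MMT dropout is censored at week 16 or the last date treatment status is known. Lapse is censored at the last date covered by EMA or timeline follow-back, or week 16.
- A sensitivity analysis counts loss as lapse.

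The investigators should reconcile the passages in section 1.9 A and B by defining when MMT dropout has occurred, how a lapse known only from a screen is dated, how prescribed opioids are treated, and how participants using opioids at baseline are handled. Those definitions are theirs to set.

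In section 1.6 A, exempt these two models from the covariate statement for characteristics measured after randomization, and describe those characteristics by arm.

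Cost: two or three sentences for the analysis, the definitions, and one extra summary, using standard software and no new data. Precision does not improve: the interval for HR 0.5 stays at about 0.13 to 1.9.

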Data will be received by the REDCAP system. Data access between the REDCap database and the web server is encrypted and restricted to a monitored port. All REDCap data, which is displayed or captured by the user interface, is encrypted for security. Within REDCap all data transactions including inserts, updates, deletions, import/export and reporting are logged. The EMA system in this study deployed via REDCap will reside in a HIPAA compliant protected space. The REDCap production and development servers use encrypted drives. Physical hardware will be secured in a locked facility.

The data will only be accessible to study investigators and staff. The data will be processed by an already developed REDCap program that formats the data as a "long file" with one row per time point per individual participant. The investigators will employ linear mixed models to test the effects of MORE vs. the control condition on substance use, craving, pain, and other study variables. The treatment X time interaction will be the main fixed effect of interest. Models will include a random intercept, as well as a random slope if warranted by model fit statistics. Auto-correlation between repeated measures will be modeled as a first-order autoregressive function. We will also compute within-group linear mixed models examining mindfulness practice duration as a predictor of clinical outcomes.

Substance use history (Baseline). We will use the PhenX Toolkit-Substance Abuse and Addictions Core Tier 1 Collection² to gather self-report information on lifetime use of opiates, alcohol, tobacco and substances, and past-30 day use of all substances.

Current substance use (Baseline, 8 weeks, and 16 weeks). We will utilize a urine screen that tests for buprenorphine and methadone (to provide corroboration of MAT engagement and compliance) and additional

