4.3 Subject Randomization

Since MORE is a closed group, we will randomize cohorts of 10-16 participants (depending on speed of recruitment) at each site to TAU or MORE with block randomization. Once we recruit at least 10 participants at a particular clinic, we will randomize participants to MORE or TAU, and the MORE group will begin. We estimate that we will recruit at least 10 participants per month.

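### The plan does not specify baseline adjustment for the pain, craving and affect visit scales; adding it would modestly tighten exploratory effect sizes if baseline and follow-up scores are moderately correlated

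*Combined protocol and SAP*

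**What the plan says.** Section 6.1 A describes the between-arm analysis in one phrase: the team will "examine group differences (e.g., chi-square, ANOVA, t-tests) to explore possible effects". Section 6.1 B gives the purpose: "Since this is a pilot study to determine feasibility and preliminary effect size". No effect size, SD or power stands behind the sample of 31.

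Section 1.9 B schedules BPI severity and interference, the adapted craving scale and the PANAS at baseline, 8 and 16 weeks, so a baseline score is already collected for each.

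Four other places bear on how baseline might be used:

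- Section 1.1 B hypothesises that "the MORE group will have greater decreases in pain severity and pain interference than the TAU group", and Section 1.3 lists "changes in pain severity and intensity" among the secondary outcomes. Both suggest a change score, for pain only.
- The EMA part of Section 1.9 B plans linear mixed models "to test the effects of MORE vs. the control condition on substance use, craving, pain, and other study variables", and adds: "The treatment X time interaction will be the main fixed effect of interest". It does not say whether the visit scales are included, or whether the arms have separate baseline means.
- Section 1.6 A says that clinic-treatment characteristics (methadone dosage, take-home dosing, attendance at clinic and counselling) "will be documented for all study participants and entered as covariates in the analyses". The baseline outcome score is not among them.
- Section 4.3 says "we will randomize cohorts of 10-16 participants (depending on speed of recruitment) at each site to TAU or MORE with block randomization".

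**The concern.** For each visit scale the text allows at least three estimates: a t-test or ANOVA on the follow-up score, a comparison of changes from baseline, and a treatment-by-time contrast from a mixed model. It does not say which will be reported, and it specifies none that adjusts for the baseline score.

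Two things are at stake, both modest. First, in a trial this small the arms can differ noticeably at baseline by chance. The follow-up comparison and the change comparison then give different effect sizes, so the result depends on which is picked. Second, if baseline and follow-up scores are moderately correlated, an unadjusted analysis gives a wider interval than the data need to give. Both touch a purpose the plan states, a preliminary effect size for a larger trial.

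**Working it through.** **The plan's own figure.** N=31 has no formula behind it, so nothing can be reproduced beyond 15 + 16 = 31 (Sections 1.3 and 1.5), which agrees.

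**Inputs.** Randomised: 15 v 16. Follow-up targets are 80% at 8 weeks and 75% at 16 weeks, and the 16-week benchmark is 50% (Section 1.3). Of 31 these give 24.8, 23.25 and 15.5, taken as 12 v 13, 11 v 12 and 8 v 8. The baseline-to-follow-up correlation r is not in the documents; I assume 0.3 to 0.7. The pain entry threshold in Section 4.2 could lower it for pain. The SD is taken as equal at both times.

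**Dependence on the analysis picked.** With complete data, the follow-up difference minus the change difference equals the baseline difference exactly. At 15 v 16 its SD is sqrt(1/15 + 1/16) = 0.359 SD. With normal scores, P(|difference| > 0.5 SD) = 0.164. Given a baseline difference d, the follow-up estimate shifts by r × d and the change estimate by −(1−r) × d. For d = 0.5 SD:

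- r=0.3: +0.15 and −0.35 SD
- r=0.5: +0.25 and −0.25 SD
- r=0.7: +0.35 and −0.15 SD

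Conditioning on baseline removes this shift. The arm effect is then the same whether the outcome is the score or its change, so the pain hypothesis is still answered.

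**Precision.** Let s = sqrt(1/n1 + 1/n2) and N = n1 + n2. The 95% half-widths in SD units are:

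- follow-up t-test: t(N−2) × s
- change score: t(N−2) × s × sqrt(2(1−r))
- baseline-adjusted: t(N−3) × s × sqrt((1−r²)(1 + 1/(N−4)))

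Example, 15 v 16 and r=0.5. The t-test gives 2.045 × 0.3594 = 0.735. The change score gives the same, because 2(1−0.5) = 1. Adjusted: 2.048 × 0.3594 × sqrt(0.75 × 28/27) = 0.649. The reduction is 1 − 0.649/0.735 = 11.7%.

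Half-widths as t-test / change / adjusted:

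| Analysed | r=0.3 | r=0.5 | r=0.7 | Gain at r=0.5 |
|---|---|---|---|---|
| 15 v 16 | 0.735 / 0.870 / 0.715 | 0.735 / 0.735 / 0.649 | 0.735 / 0.569 / 0.535 | 11.7% |
| 12 v 13 | 0.828 / 0.980 / 0.811 | 0.828 / 0.828 / 0.736 | 0.828 / 0.641 / 0.607 | 11.1% |
| 11 v 12 | 0.868 / 1.027 / 0.852 | 0.868 / 0.868 / 0.774 | 0.868 / 0.672 / 0.638 | 10.9% |
| 8 v 8 | 1.072 / 1.269 / 1.073 | 1.072 / 1.072 / 0.974 | 1.072 / 0.831 / 0.803 | 9.2% |

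Against the t-test, adjustment breaks even at r = 0.20, 0.22, 0.24 and 0.30 for the four sizes; below that the interval is slightly wider. Against the change score it is narrower up to r = 0.92, 0.90, 0.89 and 0.82. A simulation at 12 v 13 and r=0.5 gave mean half-widths of 0.815, 0.818 and 0.724, again about 11%.

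**Adding further terms.** Cohorts of 10 to 16 make 2 or 3 cohorts from 31 people, hence 1 or 2 cohort terms. With two terms and no cohort effect, the r=0.5 gain is 11.2% at 15 v 16 and 6.8% at 8 v 8. In a simulation of 8 v 8 with random loss across three cohorts, the baseline-plus-cohort model was about 6% wider than the t-test at r=0.3, about 4% narrower at r=0.5, and about 3% wider than the change score at r=0.7.

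Adding four clinic-treatment covariates as well, assumed unrelated to outcome (a pessimistic case), changes the width against the t-test at r=0.5 by −2.3%, +2.5%, +5.1% and +29.3% at the four sizes.

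**The case against.** The named tests are introduced as examples, and Section 1.6 A already commits to covariates. A reader might infer that the plan rules out conditioning on baseline. The documents do not support that; they are silent on it.

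A reader might also infer that the Section 1.9 model is for EMA data only, or that it cannot condition on baseline. Neither is established. Its stated scope extends to other study variables, and Sections 1.1 A and 1.9 B describe affect on the PANAS, a visit scale, as trajectories. A treatment-by-time model with free baseline means in each arm reduces to the change score for complete data. One with a common baseline mean conditions on baseline in effect. The text does not say which is meant. So what stands is a lack of specification, not a wrong choice.

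The benefit also depends on an unknown r, and no decision rests on it. Progression is judged on recruitment, retention and follow-up, and the larger trial is already listed at N=150. Even adjusted, the half-width at 15 v 16 and r=0.5 is about 0.65 SD, above the d=.63 cited for pain severity in Section 1.4. All of this stands, and it sets the size of the point.

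Finally, the widths assume independent participants. MORE is delivered in closed groups, so the absolute widths may be optimistic for every method.

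**Conclusion.** The point holds as a minor one: no section specifies adjustment of the visit scales for the baseline score already collected. At an assumed r of 0.5, baseline adjustment alone narrows the interval by about 12% at 15 v 16, 11% at 12 v 13 and 9% at 8 v 8 against either the t-test or the change score. It also removes the dependence of the estimate on chance baseline imbalance, and that benefit does not rest on r being moderate. At r=0.3 the gain over the t-test is 2.7% at 15 v 16 and nil at 8 v 8. At r=0.7 the gain over the change score is 6.0% and 3.3%.

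A reader might infer that the unadjusted comparisons are biased or have the wrong type I error. Under randomisation neither follows. The feasibility milestones, N=31 and the time-to-lapse and time-to-dropout outcomes are unaffected.

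**What to change.** In Section 6.1 A, state that each visit scale (BPI severity, BPI interference, craving, PANAS positive and negative) is compared by ANCOVA on the baseline score, or by a mixed model of the 8- and 16-week scores with arm, visit, arm-by-visit and baseline score. Report the adjusted MORE minus TAU difference with its 95% CI at each visit. If the Section 1.9 model is meant for these scales, say so and constrain the arms to a common baseline mean, which has the same effect.

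Put randomisation cohort in a sensitivity analysis. Blocking within cohort is a reason to look at it, but at low follow-up it can use up the gain. Treat the Section 1.6 covariates the same way for these scales, restricted to values from before randomisation, since attendance and dosing recorded later may be affected by arm.

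Cost: no new data and one degree of freedom, with no gain over the t-test if r is below about 0.2 (15 v 16) to 0.3 (8 v 8). Moving the Section 1.6 covariates alters a stated commitment, so it should be written as a deliberate change.
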